To answer research question 2, we will use the BAC-C questionnaire.¹⁵ The BAC-C is a measure that can be used by parent of children aged 4 to 11 to screen and monitor mental health difficulties for children. Descriptions are given for 20 behaviours and feelings, and parents are asked to assess if the behaviour occurred in the last 4 to 6 months. The test takes 5 minutes to complete. The total raw problem score ranges between 0 and 40, with high scores indicating that more problems are present.

Secondary outcome: Parent–child relationship and bonding

To answer research question 3, we will use the closeness scale from the CPRS questionnaire.¹⁶ This is a parent self-report questionnaire that aims to assess the quality of a parent–child relationship. The pilot will focus on the items of the CPRS that aim to assess closeness by assessing level of warmth, affection, and open communication. There are 10 outcomes that measure positive aspects of the relationship. The total score will range between 10 and 50, with higher scores indicating that a parent feels higher levels of closeness. The questionnaire will take no more than 5 minutes to complete.

Data collection

We will survey participants assigned to the treatment and waitlist treatment group **three times**: at baseline; at endline when the delivery of the programme is completed; and in a follow-up which will take place roughly two months after delivery is completed. The follow-up window is two months because this is hypothesised to provide ample time for outcomes to emerge and allows

¹⁴ Kendall S. & Bloomfield L. (2005). TOPSE: Developing and validating, a tool to measure Parenting Self-Efficacy, *Journal of Advanced Nursing*. 51(2), 174–181.

¹⁵ Tarren-Sweeny, M. (2012). Brief assessment checklists. scoring and interpretation. http://www.childpsych.org.uk/BAC_scoring_and_interpretation.pdf

¹⁶ Pianta, R. C. (1992). *Child-parent relationship scale*. Unpublished measure, University of Virginia, 427.

sufficient time for the follow-up surveys to be completed in time for analysis. The endline survey was added in order to explore early emerging impact.

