Given that PACT collects TOPSE (parental self-efficacy) as part of usual practice, they will collect the questionnaire from participating parents and will share the data with IFF, while IFF research will collect data on the secondary outcome measures (i.e. BAC-C and CPRS) from participating parents through parent-administered surveys. This approach has been taken to keep data collection from participants as minimal as possible in line with ethical good practice.

Parents will be given the questionnaire to fill in on their own without PACT present.

The researchers scoring the data will not be blind to intervention allocation. If the parent reveals their allocated treatment group to the researcher, this will be recorded.

The baseline and follow-up surveys will be sent via email and IFF will follow-up with reminder emails and telephone calls. Parents in the treatment group will complete the endline survey in the final session. PACT will extend the last session by 15 minutes to give parents time to complete the survey. Parents will be encouraged to complete the survey on their own device (e.g. their phone), but PACT will provide an alternative if needed (e.g. using a PACT laptop). Parents and children in one of the Cohort 1 waitlist treatment groups will complete the endline survey during an in-person event (for more information on the event please see the [Experiment 1: Testing use of in-person events](#)). For groups not involved in-person experiment events, parents will be sent the surveys via email by IFF to complete.

The study acknowledges that the different approaches to outcome measure deployment between the treatment group and the waitlist treatment group has the potential to introduce different biases. Though PACT may not be present, the treatment group's TOPSE being organised by PACT for the baseline and endline still may influence responses, for example by increasing the likelihood of socially desirable answers. Conversely, the waitlist treatment group receiving all measures via email may increase the potential of experiencing technical issues filling in the survey or not being able to ask for clarity on questions as they will not be in regular contact with PACT.

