The primary outcome is the TOPSE score at follow-up,¹⁸ controlling for baseline TOPSE score. We will estimate the mean difference in TOPSE scores between participating families in BB4K and the waitlist treatment group participants. The primary analysis will use a mixed effects model allowing for different outcome variance between the treatment group and waitlist treatment group arms, and heteroscedastic individual-level errors. The model will control for delivery site, child age,¹⁹ and baseline TOPSE score via fixed effects. The between-cluster variation in the treatment group groups will be modelled as a random effect. The model is not powered to investigate differences in treatment effects between sites.

The analysis model will be:

$$Y_{ijk} = \beta_0 + \sum_{k=1}^3 \beta_k s_k + \gamma Y_{0ijk} + \delta X_{ijk} + \theta t_{ijk} + t_{ijk} u_{jk} + (1 - t_{ijk}) r_{ijk} + t_{ijk} \varepsilon_{ijk}$$

- Y_{ijk} is the outcome at follow up for parent i in treatment group j and sites k
- There are three sites $k= 1,2,3$
- There are $j=9$ clusters corresponding to 5 treatment group and 4 waitlist treatment groups
- Sites $k=1,2,3$
- β_k represents difference in outcomes between sites
- θ is the treatment effect.

In line with Foundation's Statistical Guidance, the analyses will follow an intention-to-treat (ITT) approach. The analysis will include all randomised children and parents in the groups to which they were randomly assigned, regardless of the treatment actually received, withdrawal from BB4K post-randomisation, or deviations in programme implementation. This principle is key in ensuring an unbiased analysis of intervention effects. The difference between the treatment and waitlist treatment groups at endline will be expressed as a standardised effect size using Hedges' g with 95% confidence intervals. The primary analysis will also include detailed descriptive analysis: histograms, means, quartiles, and standard deviations, for all measures, groups, and time points. All analysis will be scripted to allow for transparency and replication and will be uploaded to GitHub.

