If there is less than 5% missingness overall, we will undertake a complete case analysis as the primary analysis. However, it can be problematic to apply the intention-to-treat principle if parents are not able to complete the outcome surveys. To deal with missing data we will complete the following analyses. First, we will report on attrition from analysis and attrition from BB4K including reasons. Second, we will explore the extent of missingness, and then we will assess the pattern of missingness. To assess whether there were systematic differences between those who did not complete the outcome surveys and those who did, we will model missingness through a logistic

¹⁸ The follow-up measure is used instead of the endline measure to allow for ample time for outcomes to materialise.

¹⁹ As we stratify (block) by region and age.

regression model at follow-up as a function of key covariates, including treatment, age of child, and region to assess if any covariates are associated with missing data.

For each outcome measure, we will address any item non-response by using a mean of the completed items.

If values on covariates are missing and the overall percentage of the missing covariate is over 5% and smaller than 40%, we will use multiple imputation of missing covariates.

Secondary analysis

To assess impact for the secondary outcomes (i.e. child behaviour and parent–child relationship bonding) we will employ the same principles as the primary outcome analysis.

Early impact analysis using the endline survey

To explore the timing of when outcomes can be expected to materialise, and to capitalise on existing contact with treatment group participants still being in regular contact with the programme (assuming this will support treatment group response rates as low response rate to the surveys is a key risk to the evaluation), an endline survey will be deployed once the treatment groups complete the BB4K programme.

Those in the treatment group will complete the endline survey at the end of the final BB4K session. The waitlist treatment group will be sent the endline survey to complete via email.

Early impacts will be assessed using the same analysis strategy outlined for the primary outcome analysis.

Subgroup analysis

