Treatment group celebration event: PACT will host an in-person event with one of the Cohort 1 treatment groups (selected by IFF using a random number generator) during the follow-up survey collection period at the end of September 2024. All parents and children who took part in the group will be invited via email to attend the ‘coffee morning’ celebration event and come back together a few months after their last session to reconnect and reflect on their successes.

Waitlist treatment group introduction event: PACT will host an in-person event with one of the Cohort 1 waitlist treatment groups during the endline survey collection period at the end of September 2024. IFF will randomly select the groups using a random number generator. All parents and children from one of the waitlist treatment groups, will be invited via email to attend the ‘coffee morning’ introductory event and come together to meet for the first time and learn more about what BB4K will entail.

PACT will host both events at the same location where the groups sessions are held. Events will be hosted during school hours to ensure accessibility, familiarity, and available childcare. Children will not be required to attend but parents may wish to bring along those under school age. PACT will provide tea, coffee, and cakes to encourage families to attend.

IFF will issue the follow-up survey to both groups a week before the event. During the events two researchers from IFF Research will speak to the groups about the importance of their involvement in the evaluation. They will bring laptops and offer to help parents complete the survey in-person during the event. Parents who do not attend the event and do not complete the survey following the email invite and two reminders, will receive a phone call from an IFF telephone interviewer, asking the parent to complete the survey over the phone.

For groups in Cohort 2 – not involved in this experiment – surveys will be administered by email at the time indicated in the project timetable.

Reporting results: The interim and final reports will discuss the results of Experiment 1, specifically, the effectiveness of the celebration groups by comparing response rates in the treatment group participating in the experiment to response rates in the treatment group not participating in the experiment, and similarly for the waitlist treatment groups.

Experiment 2: Testing use of incentives

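### The primary outcome is TOPSE at follow-up, but the Primary analysis section ties Hedges' g and its 95% CI to the earlier endline survey

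*Protocol*

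**What the plan says.** In the protocol, under Analysis plan, Primary analysis, the outcome is defined by wave: "The primary outcome is the TOPSE score at follow-up", adjusted for the baseline score. In the list under the model equation, Y "is the outcome at follow up for parent" i, and θ is the treatment effect from that model. Footnote 18 gives the reason: "The follow-up measure is used instead of the endline measure to allow for ample time for outcomes to materialise". RQ1 places the primary comparison five months after randomisation.

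Later in the same section comes the only sentence there on a standardised effect size: "The difference between the treatment and waitlist treatment groups at endline will be expressed as a standardised effect size". Its measure is Hedges' g, and a 95% interval is to accompany it.

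The Data collection section makes the two waves distinct. After baseline, endline is taken once delivery has finished, and follow-up comes about two months after that. Each wave has its own row in the schedule table. Endline also has its own analysis, under Early impact analysis using the endline survey.

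On Experiment 1, the Evaluation experiments section says that the events test follow-up completion in Cohort 1. It places the waitlist event "during the endline survey collection period at the end of September 2024", while the Data collection section says that parents and children in one Cohort 1 waitlist group "will complete the endline survey during an in-person event".

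**The concern.** One section gives two instructions about when the primary result is measured. An analyst who follows the effect-size sentence would compute g and its interval from the wave that the protocol has set aside for exploring early impact. Three things make this more than a cosmetic slip.

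- **Use.** The minimum detectable effect size, 0.79, is in standard deviation units. Readers judging evidence of promise would naturally set g beside it.
- **Data quality.** Treated parents complete endline in the final session run by the delivery organisation. The Data collection section itself warns that the organisation's role in TOPSE at baseline and endline may encourage socially desirable answers.
- **Reach.** The secondary outcomes are to be analysed on the same principles, and RQ2 and RQ3 are also set at five months.

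Two waves with conflicting instructions also leave room to choose the wave for g after the data are seen.

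**Working it through.** No sample-size or power figure bears on the point. The one plan figure to reproduce is RQ1's five months after randomisation. The check asks which survey wave meets it.

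**Inputs**
- Cohort 1 randomisation: April 2024 (Randomisation text) or April–May 2024 (Randomisation table).
- Cohort 2 randomisation: September 2024 (text) or August–September 2024 (table).
- Cohort 1 surveys (Data collection table): endline July–August 2024, follow-up September–October 2024.
- Cohort 2 surveys (same table): endline December 2024–January 2025, follow-up February–March 2025.

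**Formula.** Months after randomisation = survey month − randomisation month. Where randomisation spans two months, window start is paired with window start and end with end. The extremes are (first survey month − last randomisation month) and (last survey month − first randomisation month).

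| | Endline | Follow-up |
|---|---|---|
| Cohort 1, April–May: paired | Jul − Apr = 3; Aug − May = 3 | Sep − Apr = 5; Oct − May = 5 |
| Cohort 1, April–May: extremes | 2 to 4 | 4 to 6 |
| Cohort 2, September | Dec − Sep = 3; Jan − Sep = 4 | Feb − Sep = 5; Mar − Sep = 6 |
| Cohort 2, August–September: paired | Dec − Aug = 4; Jan − Sep = 4 | Feb − Aug = 6; Mar − Sep = 6 |
| Cohort 2, August–September: extremes | 3 to 5 | 5 to 7 |

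Follow-up reproduces the five months: 5 in Cohort 1, and 5 to 6 in Cohort 2 with a September randomisation. Endline does not, at 3 and at 3 to 4. Endline reaches five months only at the extreme for Cohort 2, with an August randomisation and a January response.

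**Gap between the waves.** Sep − Jul = 2 and Oct − Aug = 2 in Cohort 1; Feb − Dec = 2 and Mar − Jan = 2 in Cohort 2. An effect size taken at endline is therefore about two months early in both cohorts.

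**Primary analysis, item by item**
- Primary outcome: follow-up.
- Outcome variable in the model, and hence θ: follow-up.
- Footnote 18: follow-up in preference to endline.
- Regression for missing data: follow-up.
- Hedges' g with its 95% interval: endline.

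Only the last departs from the rest.

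**Experiment 1 label.** The waitlist event is at the end of September 2024. That is Sep − Aug = 1 month after the month in which the Cohort 1 endline window closes, and inside the September–October follow-up window. The Experiment 1 text names follow-up completion as the target, dates the treatment-group event to the follow-up period at the same time, and has the evaluator issue the follow-up survey to both groups a week before. The early-impact section has the waitlist group receive endline by email. Against these stand the two endline labels, one in the description of the waitlist event and one in Data collection.

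**The case against.** The strongest reply is that this is one wrong word and that the context corrects it. Everything else defining the primary result is at follow-up, so the primary estimate and its test are not in doubt. That stands. A reader might infer that the primary analysis as a whole is aimed at the wrong wave. The document does not support this, because θ comes from a model whose outcome is the follow-up score. Nor does the protocol call g its headline result.

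It could also be said that endline is used loosely for the end of the study. That does not stand. The protocol defines endline and follow-up as different surveys, and a footnote in this very section contrasts them.

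Nor does the possible existence of a separate statistical analysis plan answer the point. The protocol does not leave the time point open; it states one that contradicts its own primary outcome.

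On Experiment 1, a reader might infer that one Cohort 1 waitlist group would supply its endline data in late September, out of step with the treated arm. The document does not establish this. The instruction to issue the follow-up survey to both groups and the July–August endline row in the schedule both say otherwise, so the two labels are an inconsistency and not a plan to collect endline late. It is also tempting to say that a single slip produced both problems. The protocol gives no evidence of a common cause.

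**Conclusion.** The point holds for the standardised effect size. Followed as written, Hedges' g and its 95% confidence interval would describe the endline wave, about two months before the primary time point and at roughly 3 to 4 months after randomisation instead of 5 to 6. It would rest on a survey that treated parents complete in their final session. The treatment effect θ is unaffected. The error may carry to the two secondary outcomes through the shared analysis principles.

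The conclusion rests on the scheduled calendar windows being kept and on the two wave names meaning what the Data collection section says. How far g would differ between the waves cannot be worked out from the document. Because the sentence gives a wrong instruction for reporting the primary outcome, it should be corrected before analysis. The Experiment 1 labels are a minor matter of consistency.

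**What to change.** 1. In the Hedges' g sentence under Primary analysis, replace endline with follow-up.
2. State that an endline g is reported only under the early-impact analysis, and that the secondary outcomes also take their effect size at follow-up.
3. Reconcile the wave label for the late-September 2024 Cohort 1 waitlist event in Data collection and in Experiment 1 with the schedule table, the stated aim of Experiment 1 and the instruction to issue the follow-up survey to both groups. State that both Cohort 1 waitlist groups receive the endline survey in July–August 2024 as scheduled. Cohort 2 keeps its December 2024–January 2025 endline.

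The cost is wording only. No survey, sample size or model changes. How g is computed from the model is a separate choice that can be left to the statistical analysis plan.

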To limit the effect of these factors, anonymity and confidentiality are emphasised in communication with participants, and clear standardised instructions are provided. Likewise, feedback on the experience of using the surveys will be collected as part of the study and a review of selected outcome measures will occur between Cohort 1 and Cohort 2 (for details, see the following section).

Cohort 1 parent–child pairs will complete the baseline survey between April and May 2024, the endline between July and August 2024, and the follow-up between September and October 2024. Cohort 2 parent–child pairs will complete the baseline survey in September 2024, the endline between December 2024 and January 2025, and the follow-up survey between February and March 2025.

	Cohort 1		Cohort 2	
	Treatment (2 groups)	Waitlist treatment (2 groups)	Treatment (3 groups)	Waitlist treatment (2 groups)
Baseline survey	Apr–May 24	Apr–May 24	Sep 24	Sep 24
Delivery	May–Jul 24 (2 groups)	Jan–Mar 25 (2 groups)	Sep–Dec 24 (3 groups)	Mar–May 25 (2 groups)
Endline survey	Jul–Aug 24	Jul–Aug 24	Dec 24–Jan 25	Dec 24–Jan 25
Follow-up survey	Sep–Oct 24	Sep–Oct 24	Feb–Mar 25	Feb–Mar 25

Review of outcome measures before they are used with Cohort 2

It is important to note that measuring outcomes for children and young people who have experienced domestic abuse can be a challenging task. While the selected measures have been used with a general population, these are not validated specifically for this group. Therefore, we will review the suitability of using the secondary outcome measures with Cohort 1. As part of this, we will review the ease of administration of the self-report surveys, including take up and time needed for administration with Cohort 1. We will also assess whether the scores are normally distributed.

Following the review, a decision will be made on whether we will employ the same outcome measures with Cohort 2.

Analysis plan

The Statistical Analysis Guidance produced by What Works for Children’s Social Care is still applicable for the work of Foundations.¹⁷

Primary analysis

The pilot is designed as a cohort two-armed, randomised waitlist trial.

¹⁷ See <https://whatworks-csc.org.uk/wp-content/uploads/WWCSC-RCT-Statistical-Analysis-Guidance-V1.2.pdf>

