
Parents – Treatment
	
x8, via x1 in-person focus groups, 1 hour, July 2024
	
x8, via x1 in-person focus groups, 1 hour, Nov 2024

Children – Treatment	x8, via x1 in-person focus groups, 1 hour, July 2024	x8, via x1 in-person focus groups, 1 hour, Nov 2024
Parents – Waitlist treatment	x2, via online interviews, 45 mins, July 2024	x2, via online interviews, 45 mins, July 2024
Total	25	24

Focus groups with children and parents were chosen over one-to-one interviews to make it easier for families to engage (hosted right after scheduled BB4K session), safeguarding (hosted in a safe and familiar space and with their PACT practitioner in the building) and data protection reasons (does not require the sharing of parent/child name, contact details with IFF). The use of focus groups also aligns with the IPE research questions (pilot evaluation requiring identification of improvements, no need for in-depth individual family journey exploration), and evaluation efficiencies (ability to capture more family views across the three delivery sites compared with one-to-one discussions).

BB4K managers

Recruitment

Sampling is not required, because we are speaking to all leadership staff. To secure a convenient time for participants, our in-house specialist recruiter will reach out to participants one month ahead of fieldwork. To mitigate cancellations, at this time they will also agree a back-up time and will send a reminder two days before the scheduled appointment.

Fieldwork

We are planning to cover the following topics:

- **Implementation approach and experience:** during the interview we will use the ToC as a guide to understand how the intervention has been implemented and delivered; explore where delivery has changed from planned and the reasons for this (e.g. workforce, local context, and required adaptations), explore the level of consistency or variation in support delivered and reasons for this (e.g. workforce availability/capability, family characteristics/needs; this includes EDIE); explore views on what has worked well/less well and why, challenges/barriers and mitigations to involvement, and areas for improvement (for all, including EDIE).
- **Perceived outcomes:** whether/what outcomes emerging (including any unintended consequences), whether outcomes achieved at expected timescales, including mechanisms driving achievement of these outcomes, evidence for any outcomes achieved, reasons for

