- **Referral process:** understanding of eligibility criteria and how to refer. Views on: how the referral pathway works from their perspective, what is working well/less well; the ease/appropriateness of the online referral form and of administrator checking their information; any suggestions for improving the referral process; whether the right families are being identified and supported by BB4K; any families they referred that were not eligible; value of the intervention within the wider support available for families in their area.
- **Experience of engaging with BB4K:** relationship with BB4K team (e.g. partnership meetings); whether/how they want to hear from BB4K to maintain engagement; what has worked well/not well and what could be improved.
- **Lessons learned for moving into the future:** areas that worked well and why in their local context – including what they intend to keep, and what might have worked better and why.

Parents and children – Treatment

Recruitment

BB4K is being delivered to five groups: two in Cohort 1 and three in Cohort 2. We will invite one treatment group family to take part in a group discussion – both parents and children – after their final BB4K group session. We will support PACT Support Workers to introduce the research to families in session 5 or 6 so parents can plan to stay after their group on their final day. To maximise family participation, we will produce an informative animation introducing the research, what taking part involves and reassurances about participation. An animation helps to communicate the research to younger children, or to people who prefer watching/hearing information over reading. Paper information leaflets will also be used for all audiences. We will incentivise parents and children, with £40 per family. We will offer Love2Shop or Amazon vouchers; parents can choose.

Fieldwork

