Experiment 2 tests the use of incentives on endline survey completion with Cohort 2 only, in January 2025. Cohort 2 has three treatment groups and two waitlist treatment groups (40 families total). We will explore the effect of offering £10 incentives for endline survey completion with two treatment and two waitlist treatment groups in Cohort 2 (32 families). IFF will randomly select the groups using a random number generator.

Those groups selected will be notified of the opportunity to receive the incentive when they're invited via email to complete the survey. At the end of the survey, they will be able to select from a £10 Amazon voucher or a £10 Love2Shop voucher and asked to provide an email address to receive the voucher. Those selected for the incentive who do not respond to the email prompts will be notified of the incentive when they receive a phone call asking them to complete the survey.

Reporting results: The final report will discuss the results of Experiment 2, specifically, the effectiveness of the incentives by comparing response rates in the treatment group participating in the experiment to response rates in the treatment group not participating in the experiment, and similarly for the waitlist treatment groups.

Cost evaluation

The overall aim of the cost evaluation is to understand the additional costs and, where possible, benefits of the programme compared to if it was not delivered. Our proposed approach is to calculate **the overall cost for BB4K delivery, and the unit cost per family and per each of the three sites.**

Costs will be based on the resources needed to roll out BB4K in comparison to 'business as usual'. In line with the WWCS cost analysis guidance, we will split costs into prerequisites (e.g. access to facilities to deliver, overheads), start-up (e.g. the purchase of equipment, training staff cost, salaries) and recurring delivery costs (e.g. non-durable materials, costs for new staff).

Outside the cost evaluation we will present separately costs of parents' time, children's time, and volunteers' time

As a first step we will calculate the overall costs at BB4K level. We will ask PACT to provide information on the following cost categories:

- Staff costs: including salaries, National Insurance Contributions, pensions for all workers including temporary and contract workers; if staff don't spend all of their time on BB4K, we will ask PACT to confirm the time allocated for the year to BB4K
- Volunteer time, if any

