Outcome measures are not optimal	Low/Medium	Outcome measures do not align with the theory, are difficult to administer, or measure a change that cannot be realised within the timeline.	Our experienced team will ensure that outcome measures are fit for purpose. This includes expert assessment and consultations with PACT to allow us to select the most robust instruments.

Timeline

Dates	Activity	Staff responsible/ Leading
January to April 2024	Onboarding and set-up (including evaluation protocol, ethics and data protection)	IFF Research
April to May 2024	Cohort 1 delivery set-up, randomisation and baseline survey (2 research/treatment groups and 2 non-research/waitlist treatment groups)	IFF Research/PACT
May to July 2024	Cohort 1 group delivery (2 groups of aged 6-11s) – 8 sessions over 10 weeks	PACT
July 2024	Cohort 1 endline survey	IFF Research
June to August 2024	Implementation and process evaluation Wave 1	IFF Research
September to October 2024	Cohort 1 follow-up survey	IFF Research
January to March 2025	Cohort 1 waitlist treatment group delivery	PACT
August to September 2024	Cohort 2 delivery set-up, randomisation and baseline survey (3 research/treatment groups and 2 non-research/waitlist treatment groups)	IFF Research/PACT
August 2024	Cost evaluation data collection Wave 1	IFF Research
September to December 2024	Cohort 2 group delivery (2 groups of aged 5–11s; 1 group age 3–5)	PACT

December 2024	Cohort 2 endline survey	IFF Research
November 2024	Mid-point grant progress report	IFF Research
December 2024 to January 2025	Implementation and process evaluation Wave 2	IFF Research
January to March 2025	Interim report	IFF Research
March 2025	Cohort 2 follow-up survey	IFF Research
April 2025	Cost evaluation data collection Wave 2	IFF Research
May to September 2025	Final reporting	IFF Research

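### Cohort 2 endline: the treatment arm answers in its final session, by December, but the incentive under test is emailed in January, and the endline dates and contact routes differ by arm and need reconciling

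*Protocol*

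**What the plan says.** Two sections place the treatment arm's endline inside the last session. Data collection says: "Parents in the treatment group will complete the endline survey in the final session", with that session extended by 15 minutes. Early impact analysis using the endline survey says: "Those in the treatment group will complete the endline survey at the end of the final BB4K session". For the other arm it says: "The waitlist treatment group will be sent the endline survey to complete via email".

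The dates come from elsewhere. Data collection gives both Cohort 2 arms one window, "the endline between December 2024 and January 2025". The Timeline lists the Cohort 2 endline as December 2024. Design and the Data collection table run Cohort 2 treatment delivery from September to December 2024.

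On contact routes, Data collection attaches reminder emails and telephone calls to the baseline and follow-up surveys. It adds that groups outside the in-person events are sent surveys by email. The Experiment 1 section says that Cohort 2 surveys go by email.

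The incentive section opens: "Experiment 2 tests the use of incentives on endline survey completion with Cohort 2 only, in January 2025". It covers two of the three treatment groups and both waitlist groups. Families learn of the offer in the email invitation or, if they do not respond, in a later telephone call. The final report is to compare response rates between incentivised and other groups within each arm.

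**The concern.** The treatment arm's endline is tied to the session count, and the waitlist arm's to the calendar. Two things follow if the sections are read together.

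First, Experiment 2 is out of sequence. A parent who filled in the survey in the last session cannot be influenced by an offer made in January. The treatment-arm response rates would then mostly reflect who attended the last session, and response-rate methods are something this pilot sets out to learn about.

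Second, early impact is to use the same intention-to-treat strategy as the primary analysis, which keeps families regardless of withdrawal or treatment received. If measurement in one arm depends on attending the last session and in the other on answering an email, the arms may differ in who is measured and when. Data collection concedes bias from the different ways of administering the survey: social desirability, technical problems and no chance to ask for clarification. It does not mention different dates or dependence on attendance.

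**Working it through.** **Family counts.** Groups are of 8 pairs (Sample size/MDES calculations). Experiment 2: (2 + 2) × 8 = 32 families, out of (3 + 2) × 8 = 40 in Cohort 2. Both match the protocol. In the treatment arm, 2 × 8 = 16 families are incentivised and 1 × 8 = 8 are not.

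**Last-session dates.** The exact start day is not given, so I assume Monday starts from 2 to 30 September 2024. Last session = first session + (weeks − 1).

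- Eight sessions (ages 6–11) at the only stated pace, "8 sessions over 10 weeks", which is a Cohort 1 entry in the Timeline: + 9 weeks gives 4 November to 2 December.
- Eight sessions with no break (8 weeks): + 7 weeks gives 21 October to 18 November.
- Twelve sessions (ages 3–5) over 12 to 14 weeks: + 11 to + 13 weeks gives 18 November to 30 December.

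Every date that fits September–December delivery falls before January 2025. The in-session survey therefore precedes the January offer in all three treatment groups.

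**Gap to the endline window.** At the 10-week pace, the eight-session groups (2 × 8 = 16 of the 3 × 8 = 24 Cohort 2 treatment pairs) finish between 4 November and 2 December. That is at most 27 days, about 4 weeks, before 1 December, and at least 0. A waitlist reply on 31 January would come 60 to 88 days after those sessions. The 12-session group probably ends inside the window. Cohort 1 is little affected: treatment delivery ends in July and both arms' window is July–August.

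**Cross-check on November.** The Qualitative research table dates the Wave 2 child focus group "x8, via x1 in-person focus groups, 1 hour, Nov 2024". The section on treatment families places it "after their final BB4K group session". Children aged 3–5 are not interviewed, so it would be one eight-session group. The Timeline, however, puts Wave 2 in December 2024 to January 2025, so this supports November only weakly, and for one group of 8.

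**Who can respond to the January offer.** Assume that 60–90% of treatment parents complete in session; the protocol gives no rate.

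- Incentivised treatment families still to answer: 16 × 0.4 = 6.4 down to 16 × 0.1 = 1.6.
- Comparison group still to answer: 8 × 0.4 = 3.2 down to 8 × 0.1 = 0.8.

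The incentive could raise the treatment-arm endline response by at most 40 to 10 percentage points, on about 6 to 2 families.

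**The case against.** The strongest reply is that much of this is inference. No section states a November endline: the pace belongs to Cohort 1, and the focus-group date conflicts with the Timeline. The table with that date also puts Wave 2 waitlist interviews in July 2024, before Cohort 2 is randomised, so its dates carry little weight. This stands. A reader might infer that all 16 families in the eight-session groups are surveyed a month or two before their comparators. The documents support only a probable finish in November or the first days of December, and a gap of that length needs late waitlist replies.

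A second reply is that absent treatment parents are not necessarily lost. Data collection and Experiment 1 mention email for groups outside the events, and Experiment 2 describes email prompts and a call for selected groups. This also stands in part: the sentences are loose, but they suggest a route. A reader might infer that families who stopped attending are missing from the treatment arm alone and that the early effect is inflated. The protocol does not say so. It expects attrition especially in the waitlist arm and gives neither an absence rate nor a score difference. One Cohort 1 waitlist group is also to be surveyed at an event, so not every waitlist family is emailed.

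Third, the endline is exploratory, and in-session completion was chosen to protect treatment-arm response. That limits the consequence but does not settle the order of survey and offer.

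**Conclusion.** The sequencing conflict holds on the text. An in-session endline finished by December cannot be prompted by a January email. It would be too strong to say that Experiment 2 cannot show a treatment-arm effect: it can, but only among in-session non-completers, about 6 to 2 of 16 under the assumed 60–90% completion.

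The date and attendance point holds as a possible difference between arms in the early-impact contrast. For the eight-session Cohort 2 groups, the survey may fall 0 to about 4 weeks before the window opens, assuming a September start and the Cohort 1 pace; the gap grows if waitlist replies come late. The size and net direction of any bias are unknown.

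The primary analysis is not affected. The Primary analysis section does refer to endline when it introduces Hedges' g, and a reader might infer that the main effect size is at risk. The same section and its footnote define the primary outcome at follow-up.

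This should be corrected before Cohort 2, but it does not undermine the trial's main question.

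**What to change.** 1. Email each Cohort 2 waitlist stratum (ages 3–5 and 6–11) its endline in the same week as the matching treatment group's final session.
2. State one rule for non-completion: email and then phone every randomised treatment family that did not complete in session, whether or not it attended.
3. Correct the Cohort 2 endline dates in Data collection and the Timeline to match, and reconcile the Experiment 1 statement on email with in-session completion.
4. Either announce the incentive to the selected groups before the final-session survey, or restrict Experiment 2 and its reported comparison to families not surveyed in session. The second option leaves very few treatment families, as shown above, and the report should say so.

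Do not move the incentive to the follow-up survey. The offer covers 2 of 3 treatment groups but 2 of 2 waitlist groups, and on the primary-outcome survey that imbalance could cause differential response.

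These steps do not cure a separate gap: with both Cohort 2 waitlist groups incentivised, (2 − 2) × 8 = 0 waitlist families remain for the promised waitlist comparison.

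The cost is waitlist endline emails in two batches instead of one, a few more reminder contacts, and corrected dates. The first option in step 4 also needs the random selection of groups to be made before the first final session.
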